## 17.8. Marketing Authorization Status of Study Interventions

Study Intervention Name	Category	Authorized in ≥ 1 Country Following EU Regulation No. 536/2014	Authorized in ≥ 1 ICH Country
Sacituzumab govitecan	Study drug	No a	No a
Hydrocortisone	AxMP	Yes	Yes
Palonosetron	AxMP	Yes	Yes
Fosaprepitant	AxMP	Yes	Yes
Aprepitant	AxMP	Yes	Yes
Dexamethasone	AxMP	Yes	Yes
Olanzapine	AxMP	Yes	Yes
Loperamide	AxMP	Yes	Yes
Diphenoxylate	AxMP	Yes	Yes
Atropine	AxMP	Yes	Yes
Opium tincture	AxMP	Yes	Yes
Octreotide	AxMP	Yes	Yes
G-CSF	AxMP	Yes	Yes

AxMP = auxiliary medicinal product; EU = European Union, ICH = International Council for Harmonisation;

G-CSF = granulocyte colony-stimulating factor; Requirements for Pharmaceuticals for Human Use

a. Rationale described in Section 1.1.4

## 17.9. Risk Factors for Febrile Neutropenia

Subjects should be evaluated for risk factors of febrile neutropenia according to local guidelines or American Society of Clinical Oncology (ASCO)/European Society for Medical Oncology (ESMO)/National Comprehensive Cancer Network (NCCN) guidelines. Risk factors per ASCO guidelines are provided as an example below.

---

### Patient Risk Factors for Febrile Neutropenia

---

Age > 65 years

---

Advanced disease

---

Previous chemotherapy or radiation therapy

---

Preexisting neutropenia or bone marrow involvement with tumor

---

Infection

---

Open wounds or recent surgery

---

Poor performance status or nutritional status

---

Poor renal function

---

Liver dysfunction, most notably elevated bilirubin

---

Cardiovascular disease

---

Multiple comorbid conditions

---

HIV infection

---

HIV = human immunodeficiency virus; ASCO = American Society of Clinical Oncology

Source: Patient characteristics associated with high risk for febrile neutropenia per ASCO guidelines {Smith 2015}

## **17.10. Country-Specific Requirements**

Not applicable.

## 17.11. Amendment History

High-level summaries of the history of this study's amendments are provided in tabular form in the subsections below (from most recent amendment to oldest). Minor changes such as the correction of typographic errors, grammar, or formatting are not detailed.

Separate summary of change documents for earlier amendments are available upon request.

A separate tracked change (red-lined) document comparing the previous version of the protocol to this amendment will be made available upon the publication of this protocol.

### 17.11.1. Amendment 5 (17 December 2024)

Rationale for Key Changes Included in Amendment 5	Affected Sections
Updated European Union Clinical Trial (EU CT) number to comply with EU-Clinical Trials Regulation (CTR) requirements.	Title page
Updated to add information on study modifications after implementation of Protocol Amendment 5 (PA5). The modifications reduce the schedule of assessments for subjects remaining on treatment and terminate survival follow-up for subjects who have previously discontinued treatment.	Synopsis, Sections 3, 4, 5, and 10.1.4
Information on survival follow-up for subjects was updated with procedures following implementation of PA5.	Synopsis and Section 4.7
Information on end of study for subjects was updated with procedures following implementation of PA5.	Synopsis and Section 4.8
Updated text to align with the approval status of sacituzumab govitecan (SG) in the United States.	Sections 1.1.3 and 1.1.4
Updated safety recommendations for subjects who are at risk for complications from neutropenia.	Sections 1.1.3.3, 1.2.2, 7.5.1, 7.5.2.3, and Appendix 17.9
Updated to expand pandemic risk and mitigation plan to disasters and public health emergencies to align with recent regulatory guidance.	Section 1.2.2 and Appendix 17.7
Added text to clarify that pharmacokinetic (PK), anti-drug antibody (ADA), biomarker samples, and uridine diphosphate-glucuronosyltransferase 1A1 (UGT1A1) genotyping will not be collected following implementation of PA5. Added information for scans, tumour response data, and disease following implementation of PA5.	Sections 4.3, 10.3, 10.4, 10.5, and 10.6
Table summarizing recommendations for SG dose reductions and discontinuations for treatment-related toxicities was added.	Section 7.5.2.5
Updated text to clarify that while tumor response data will no longer be collected after implementation of PA5, subjects who continue treatment will be expected to have scans performed per standard of care.	Sections 5 and 9
Text updated to align with adverse event and suspected unexpected serious adverse reaction (SUSAR) reporting requirements and procedures.	Sections 10.2.2.2, 10.2.5, and 10.2.6
Added text to clarify that enterprise level technical and organizational controls have been developed at Gilead Sciences for the purpose of data protection.	Section 12.6

Rationale for Key Changes Included in Amendment 5	Affected Sections
Updated text to clarify that a clinical study report (CSR) will be prepared and provided to the regulatory agency(ies) and study results will be made publicly available when applicable and in accordance with local regulatory requirements.	Section 15
Minor clarifications and changes to correct typographic errors.	Throughout, as needed

### 17.11.2. Amendment 4 (09 October 2023 )

Rationale for Key Changes Included in Amendment 4	Affected Sections
A statement to clarify that the hematology and serum chemistry tests may be performed and reviewed up to 24 hours prior to scheduled study treatment administration was added	Section 4.3, Section 5 (Table 2: footnotes 'j' and 'l')
Text was updated to align with SG content library	Section 8.5
Changes from administrative amendment 3.0.1 were added to the protocol	Sections 4.6 and 7.5.2.5
Changes from administrative amendment 3.0.2 were added to the protocol	Sections 4.3, 5, (Table 2: footnote 't'), 8.3, 8.4, and 10.2.2.1
A separate page for the Sponsor Signature Page was added to the appendices to align with Clinical Trials Information System (CTIS) requirements for a consolidated and harmonized protocol	Appendix 17.11
A separate page for Amendment History and Country-Specific Requirement was added to align with EU CTR requirement	Appendix 17.9 and 17.10
A separate page for Marketing Authorization Status of Study Interventions was added to align with EU CTR requirement	Appendix 17.8
Minor changes to correct typographic errors	Throughout, as needed

1. INTRODUCTION

This statistical analysis plan (SAP) describes the statistical analysis methods and defines key elements including variable definitions for analysis of data from Study IMMU-132-11 in support of the primary analysis preceding the final analysis. This SAP is based on the study protocol Amendment 5 dated 17 December 2024. Any changes made after the finalization of the SAP will be documented in the CSR.

The purpose of this primary analysis is to summarize the efficacy and safety data for all the participants from non-small cell lung cancer (NSCLC) including adenocarcinoma and squamous cell carcinoma (SCC) cohorts, endometrial carcinoma, head and neck squamous cell carcinoma (HNSCC), and small cell lung cancer (SCLC) cohorts. These cohorts are at the proof of concept (POC) stage of the study. Additional follow-up data from participants in these POC cohorts that are beyond the primary analysis data cutoff date will be summarized in the final analysis that will be prepared once all participants have completed the study.

The biomarker analysis will be described in a separate analysis plan.

Analysis methods specified in this document take precedence over those described in the protocol should there be any difference.

1.1. Study Objectives and Endpoints

The objectives of this study are to evaluate the efficacy and the safety of sacituzumab govitecan in participants with metastatic solid tumors.

Primary Objective	Primary Endpoint
Efficacy	
Assess the ORR of sacituzumab govitecan in participants with metastatic solid tumors by Investigator's assessment according to the Response Evaluation Criteria in Solid Tumors Version 1.1 (RECIST v1.1) criteria.Objective response rate (ORR) according to RECIST v1.1 by Investigator's assessment.
Secondary Objectives	Secondary Endpoints
Efficacy/Safety/PK/ADA delineate objectives and endpoints	
Assess the ORR, duration of response (DOR), clinical benefit rate (CBR), and progression-free survival (PFS) of sacituzumab govitecan in participants with metastatic solid tumors by blinded independent central review (BICR) according to RECIST v1.1 criteria.Assess the DOR, CBR, and PFS of sacituzumab govitecan in participants with metastatic solid tumors by Investigator's assessment according to RECIST v1.1 criteria.ORR, DOR, CBR, and PFS according to RECIST v1.1 by BICR.DOR, CBR, and PFS, according to RECIS v1.1 by Investigator's assessment.Overall survival (OS).Incidence of treatment-emergent adverse events (AEs) and clinical laboratory abnormalities.Serum concentrations of sacituzumab govitecan over time and incidence of anti-drug antibody (ADA) to sacituzumab govitecan.

Assess the overall survival (OS) of sacituzumab govitecan in participants with metastatic solid tumors.Assess the safety of sacituzumab govitecan in participants with metastatic solid tumors.Assess the PK and immunogenicity of sacituzumab govitecan in participants with metastatic solid tumors.	
Exploratory Objectives	Exploratory Endpoints

1.2. Study Design

This is a multi-cohort, open-label, Phase 2 study designed to assess the efficacy and safety of sacituzumab govitecan in adult participants with metastatic solid tumors. Upon meeting the eligibility criteria, the participants are treated with sacituzumab govitecan at 10 mg/kg via intravenous infusion on Days 1 and 8 of a 21-day cycle. The original protocol included the following cohorts: non-small cell lung cancer (NSCLC: adenocarcinoma and squamous cell carcinoma [SCC]), head and neck squamous cell carcinoma (HNSCC), and endometrial carcinoma cohorts.

With Amendment 3, this is a single stage cohort evaluation for proof of concept (POC) with recalculation of sample sizes for all the cohorts. An additional cohort for small cell lung cancer (SCLC) was added. The Sponsor will evaluate the totality of efficacy and safety data at the end of the POC stage independently for each of the cohorts, and may potentially expand the HNSCC, endometrial carcinoma, and SCLC cohorts to enroll additional participants up to a total sample size of 100 to 120 participants in each selected cohort (including participants enrolled in this initial stage). In addition, OS is included as a secondary endpoint and will be assessed for all cohorts. **CCI**

1.3. Sample Size and Power

Approximately a total of 165 participants will be enrolled for the initial POC stage, that is, 30 participants from each of NSCLC (adenocarcinoma and SCC) and HNSCC cohorts, 35 participants for the endometrial carcinoma cohort, and 40 participants for the SCLC cohort. Once the efficacy bars are reached in endometrial carcinoma, HNSCC or SCLC cohort, the Sponsor may choose to expand any of these cohorts and continue to enroll additional participants, so that approximately a total of 100 to 120 participants (including participants enrolled in the initial stage) in each selected cohort will be accrued. If one or more cohorts are expanded, the total study sample size combining participants in both the POC and the expansion stages can be approximately 225 to 420 participants.

In Amendment 3, the sample size for the POC stage was not based on formal power calculation but to ensure the accuracy for the estimation of ORR. For each cohort of NSCLC, assuming the true ORR is 25%, a sample size of 30 participants will ensure the half-width of the 95% CI is ≤ 0.155 ; for the HNSCC cohort, assuming the true ORR is 22%, a sample size of 30 participants in the POC stage will ensure the half-width of the 95% CI is ≤ 0.148 ; for the endometrial carcinoma cohort, assuming the true ORR is 23%, a sample size of 35 participants will ensure the half-width of the 95% CI is ≤ 0.139 ; for the SCLC cohort, assuming the true ORR is 25%, a sample size of 40 participants will ensure the half-width of the 95% CI is ≤ 0.134 .

2. TYPE OF PLANNED ANALYSES

2.1. Interim Analysis

No formal interim analysis is planned in the current protocol amendment 5.

2.2. Primary Analysis

The primary analysis includes the efficacy and safety analyses from data in the POC stage for all cohorts. It could potentially be used for different regulatory, publication, and conferences purposes.

2.3. Final Analysis

A final analysis primarily for safety updates will be performed after all participants have completed the study.

3. GENERAL CONSIDERATIONS FOR DATA ANALYSES

Analyses pertaining to the study's primary and secondary objectives and the corresponding end points will be conducted as described in respective sections of this SAP. Any notable analyses, adjustments to analyses, or analyses not conducted due to lack of data (such as insignificant numbers of participants in subgroups) or due to other technical constraints will be noted, if included in the CSR.

Unless otherwise specified, separate analyses will be conducted by cohort. Data from participants enrolled in the 2 NSCLC cohorts before and after the removal of TROP-2 expression criterion from the protocol will be summarized separately. Additional information is provided in section 3.2. All efficacy analysis will be analyzed using the Full Analysis Set and all safety analyses will be analyzed using the Safety Analysis Set unless otherwise specified.

Analysis results will be presented using descriptive statistics. For categorical variables, the number and percent of participants in each category will be presented; for continuous variables, the number of participants (n), mean, standard deviation (StD), median, first quartile (Q1), third quartile (Q3), minimum, and maximum will be presented.

By-participant listings will be presented for all participants in the Enrolled Analysis Set/Full Analysis Set/Safety Analysis Set and sorted by participant, visit date, and time (if applicable). Data collected on log forms, such as AEs, will be presented in chronological order within the participant. The cohorts to which participants were initially assigned will be used in the listings. Age, sex at birth, race, and ethnicity will be included in the listings, as space permits.

Throughout this SAP, both study drug and study treatment refer to sacituzumab govitecan and the two terms are used interchangeably.

3.1. Analysis Sets

For each analysis set, the number and percent of participants eligible for inclusion will be summarized by cohort.

3.1.1. Enrolled Analysis Set

The Enrolled Analysis Set includes all participants who have been assigned enrollment dates. This analysis set will be used to summarize the tables of key study dates, enrollment, disposition, and eligibility criteria deviations.

3.1.2. Full Analysis Set

The Full Analysis Set includes all participants who took at least 1 dose of sacituzumab govitecan. This is the primary analysis set for efficacy analyses.

3.1.3. Efficacy Evaluable Analysis Set

The Efficacy Evaluable Analysis Set includes all participants in the Full Analysis Set who had measurable disease at baseline and at least one post-baseline tumor assessment. This analysis set will be used for the sensitivity analysis of the primary efficacy endpoint.

3.1.4. Safety Analysis Set

The Safety Analysis Set includes all participants who took at least 1 dose of sacituzumab govitecan. This is the primary analysis set for safety analyses. The Safety Analysis Set and the Full Analysis Set are the same for this primary analysis.

3.1.5. Pharmacokinetic Analysis Set

The PK analysis will be conducted on the Pharmacokinetic Analysis Set, defined as all randomized participants who received at least 1 dose of SG per the protocol and have at least 1 evaluable post-treatment serum concentration of SG, total SN-38, free SN-38, or total antibody (hRS7 IgG).

3.1.6. Immunogenicity Analysis Set

The immunogenicity analysis will be conducted on the Immunogenicity Analysis Set, defined as all randomized participants who received at least 1 dose of SG and have at least 1 evaluable posttreatment anti-SG antibody test result.

3.2. Participant Grouping

For all the safety and efficacy analyses, the data for the cohorts (i.e., NSCLC, endometrial carcinoma, HNSCC and SCLC) will be presented separately for each cohort.

The data for the NSCLC cohorts will be presented on each of the following groups:

- 1) all NSCLC participants (adenocarcinoma and squamous cell cancer cohorts combined) enrolled in original protocol and protocol amendment 1, where TROP-2 expression criteria is mandated
- 2) adenocarcinoma cohort enrolled under amendments 2 and 3
- 3) squamous cell cohort enrolled under amendments 2 and 3

Please note: TROP-2 expression requirement was removed in amendments 2 and 3. Therefore, NSCLC participants enrolled before the removal of TROP-2 expression criteria were grouped separately.

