### **11.3. Safety Analyses**

All subjects administered at least 1 dose of sacituzumab govitecan will be included in the evaluation of safety.

Safety will be evaluated based on AEs, standard safety laboratories (CBC with differential), serum chemistries, and urinalysis (if clinically indicated).

The total amount of study drug and number of cycles and doses received will be summarized by the histological cohort.

The frequency and severity of AEs, classified by Medical Dictionary for Regulatory Activities (MedDRA), will be summarized overall and by histological cohort using MedDRA Preferred Term (PT) and System Organ Class (SOC). An AE that occurs more than once within each subject will be counted only once in the summaries, using the worst NCI-CTCAE grade and relationship category. AEs will be consolidated using the worst NCI-CTCAE grade and relationship category observed for classification into each MedDRA SOC summary.

AEs leading to death or to discontinuation from treatment as well as all SAEs will be summarized or listed separately. A listing of all death information will be generated. The reasons for study treatment discontinuation will also be summarized for each histological cohort.

Routine safety laboratories, based on hematology and routine serum chemistry data (glucose, creatinine, BUN, total bilirubin, AST, ALT, LDH, uric acid, alkaline phosphatase, serum albumin, total protein, sodium, potassium, calcium, chloride, bicarbonate, magnesium, and phosphorus), will be summarized using values at each visit and change from baseline using descriptive statistics for each histological cohort.

Laboratory test results for platelets, neutrophils, white blood count, lymphocytes and hemoglobin will be graded according to NCI-CTCAE severity grade. The worst NCI-CTCAE grade observed on-treatment will be tabulated for each laboratory parameter and presented in a frequency table by baseline grade. For parameters for which an NCI-CTCAE scale does not exist, the proportion of subjects with abnormal values will be summarized by histological cohort.

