7.1.6.1. Summaries of AE Incidence

Treatment-emergent AEs, SAEs, grade 3 or worse TEAEs, treatment-related TEAEs, TEAEs leading to study drug discontinuation, TEAEs leading to study drug interruption, TEAEs leading to dose reduction, TEAEs leading to death, protocol - defined AEs of special interest and other safety observations will be summarized based on the Safety Analysis Set. SAEs occurring beyond reporting period may be listed.

A brief, high-level summary of the number and percent of participants who experienced at least 1 TEAE in the categories described below will be provided by cohort. All deaths observed in the study will also be included in this summary.

The number and percent of participants who experienced at least 1 TEAE will be provided and summarized by SOC, PT and cohort:

- TEAEs
- TEAEs with Grade 3 or higher
- TE treatment-related AEs
- TE treatment-related AEs with Grade 3 or higher
- TE SAEs
- TE treatment-related SAEs
- TEAEs leading to discontinuation of study drug
- TEAEs leading to death
- TE Treatment-related AEs leading to death
- TEAEs leading to interruption of study drug
- TEAEs leading to dose reduction

For AE categories described below, summaries will be provided by SOC, PT, maximum severity and cohort:

- TEAEs
- TE Treatment-related AEs

- TE Treatment-related AEs with Grade 3 or higher

For AE categories described below, summaries will be provided by PT and cohort:

- TEAEs reported by $\geq 10\%$ participants
- TE treatment-related AEs reported by $\geq 5\%$ participants
- TEAEs with CTCAE Grade 3 or higher reported by $\geq 2\%$ participants
- TE SAE reported by $\geq 2\%$ participants
- TEAEs leading to dose reduction
- TEAEs leading to interruption of study drug
- TEAEs leading to discontinuation of study drug

Multiple events will be counted only once per participant in each summary. Adverse events will be summarized and listed first in alphabetic order of SOC, and then by PT in descending order of total frequency within each SOC. For summaries by severity grade, the worst severity will be used for those AEs that occurred more than once in an individual participant during the study.

In addition to the above summary tables, all TEAEs, TE SAEs, TE treatment-related AEs, and TE treatment-related SAEs will be summarized by PT only, in descending order of total frequency.

In addition, data listings will be provided for the following:

- AEs, indicating whether the event is treatment emergent
- SAEs
- Deaths

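### Does the SAP drop the all-cohort adverse event summary that Protocol 11.3 asks for?

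*SAP*

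**What the plan says.** Protocol 11.3 says that the frequency and severity of AEs "will be summarized overall and by histological cohort using MedDRA Preferred Term (PT) and System Organ Class (SOC"). Other items in that section are requested by cohort alone. On exposure: "The total amount of study drug and number of cycles and doses received will be summarized by the histological cohort". On stopping treatment: "The reasons for study treatment discontinuation will also be summarized for each histological cohort". On who counts: "All subjects administered at least 1 dose of sacituzumab govitecan will be included in the evaluation of safety".

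SAP 3 makes analysis by cohort the default unless otherwise specified, and SAP 3.2 repeats this: "For all the safety and efficacy analyses, the data for the cohorts (i.e., NSCLC, endometrial carcinoma, HNSCC and SCLC) will be presented separately". It then splits NSCLC into three groups: everyone enrolled while TROP-2 selection applied, and the later adenocarcinoma and squamous cohorts.

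SAP 7.1.6.1 describes the main AE tables as ones that "will be provided and summarized by SOC, PT and cohort". For severity, "summaries will be provided by SOC, PT, maximum severity and cohort". It adds further tables of treatment-emergent AEs (TEAEs) that "will be summarized by PT only, in descending order of total frequency".

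SAP 7.6 states that the safety analyses do not depart from the protocol. SAP 1 gives the SAP precedence where the two documents differ.

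**The concern.** Within Protocol 11.3 the word *overall* appears to be deliberate. It is attached to AEs and left off exposure, discontinuation reasons and laboratory values. The SAP's matching tables name SOC, PT, severity and cohort, and no all-cohort column is written down. Read strictly, the SAP omits something the protocol requires, the precedence clause makes the omission final, and SAP 7.6 tells the reader that nothing changed.

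At stake would be the trial's own pooled safety rate. All cohorts start the same drug at the same dose and schedule, so a pooled rate is a natural summary, and single cohorts of 30 to 40 say little about uncommon events. The pooled rates in Protocol 1.1.3.3 come from other studies. It also looks unsettled whether a pooled column would include the roughly 40 NSCLC participants enrolled before Amendment 2, whose data Protocol 11.1 allows, but does not require, to be analysed with later participants.

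**Working it through.** **1. Is a total excluded, or only not mentioned?**

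| Item | Protocol 11.3 | SAP |
|---|---|---|
| AE frequency by SOC/PT | overall and by cohort | by cohort; no total named (7.1.6.1) |
| AE severity by SOC/PT | overall and by cohort | by cohort; no total named (7.1.6.1) |
| Sort order of PTs | not stated | by total frequency (7.1.6.1) |
| TEAEs by PT alone | not requested | no cohort term (7.1.6.1) |
| TEAEs by age group | not requested | Safety Analysis Set, no cohort term (7.1.7.1) |
| Who is included | everyone dosed | everyone dosed (3.1.4) |

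Nowhere does the SAP say cohort *only*. Showing cohorts separately is compatible with separate columns plus a total. The sort rule needs a total frequency of some kind. These signs do not specify an overall column, and none covers severity, but they leave omission unproven. The table shells, where total columns are normally set out, are not in the documents.

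**2. If no total is printed, is the overall summary lost?**

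For a given SOC or PT row, let x(g,k) be the number of participants in group g whose worst grade is k, and n(g) the group size. Then

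overall rate at grade k = Σ x(g,k) / Σ n(g).

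This is exact if each participant belongs to one group and is counted once per row.

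- *Counted once:* SAP 7.1.6.1 counts multiple events once per participant and uses the worst grade.
- *No overlap:* the six groups are early NSCLC, later adenocarcinoma, later squamous, endometrial, HNSCC and SCLC.
- *Nobody left out:* SAP 3.2 describes the later NSCLC groups as enrolled under Amendments 2 and 3. The synopsis estimates last enrolment at 30 May 2023, and Amendment 4 is dated 09 October 2023, so no NSCLC participant should fall outside the groups.

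Illustration with planned sizes (Protocol 3, SAP 1.3) and assumed counts near the 10.6% Grade 3–4 diarrhea rate of Protocol 1.1.3.3:

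- Sizes: 30 + 30 + 30 + 35 + 40 = 165, which reproduces the stated proof-of-concept total.
- Events: 3 + 3 + 3 + 4 + 4 = 17, and 17/165 = 10.3%.
- Adding about 40 early NSCLC participants with an assumed 5 events: 22/205 = 10.7%.

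**3. Is precision lost?**

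With zero events the upper exact two-sided 95% limit is 1 − 0.025^(1/n): 11.6% at n = 30, 10.0% at 35, 8.8% at 40, 2.2% at 165 and 1.8% at 205. Near 10.6%, 3/30 gives 2.1–26.5% and 17/165 gives 6.1–16.0%. These figures compare a cohort rate with a pooled rate, treating different tumor types as one sample. They do not measure a loss, because the 17 and the 165 can be read off the cohort columns, and the SAP plans no AE intervals.

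**4. Does anything depend on the pooled rate?**

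SAP 3 makes the presentation descriptive, and SAP 6.1.2 states no hypothesis for this stage. Under SAP 1.2 the sponsor weighs efficacy and safety independently for each cohort when considering expansion. A pooled AE rate enters none of these.

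**5. Who would be in a total column?**

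SAP 7.1.6 bases the AE summaries on the Safety Analysis Set, which SAP 3.1.4 defines as everyone who took at least one dose. A total on that set therefore includes the early NSCLC participants. Showing them as their own group, as SAP 3 and 3.2 require, does not conflict with that.

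**The case for a change.** The strongest case is textual. The protocol singles out AEs for an overall summary, and the SAP's two matching table descriptions do not contain one. The sort rule does not define a pooled group. The PT-only tables, even if pooled, carry neither SOC nor severity. The age-group table is split by age with no stated total, and SAP 3.4 introduces it in words that may mean each cohort or all of them together. The precedence clause settles which text governs, but it does not make SAP 7.6 accurate. Curing the mismatch would take one column or one sentence.

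Most of this stands as a description of the wording: the SAP does not expressly commit to the overall column. Two things do not stand. First, the statement in SAP 7.6 is not shown to be false. It would be false only if the total is in fact omitted, and the text leaves that open. This SAP also covers the primary analysis, while SAP 2.3 plans a later final analysis mainly for safety updates, and Protocol 11.3 does not say at which analysis the overall summary must appear. Second, a cheap correction is not a reason for one when the information is already in the planned output.

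**Conclusion.** No change is needed. This is a gap in wording that a programmer would ordinarily fill with a total column on the Safety Analysis Set. If that were not done, a reader could still rebuild the overall frequency and severity exactly from the full SOC/PT and maximum-severity tables. No endpoint, interval, test or decision would differ. The shift from 165 to about 205 when early NSCLC participants are included concerns a column whose membership SAP 3.1.4 already fixes.

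This rests on three assumptions: the six groups cover everyone dosed, as the dates indicate; the full SOC/PT and severity tables are produced as planned, without a frequency cut-off; and actual cohort sizes may differ from the planned ones, which affects the illustration but not the additivity. The conclusion would be different if a pooled AE rate fed a stopping rule, a formal comparison or a planned interval, but the documents contain no such use.
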